Study Objectives	
Primary objectives:
 
1. To characterize cigarette consumption behavior (cigarettes per day and smoking topography) before, during and after a switch from usual brand (UB) to very low nicotine (VLN) cigarettes for 6 weeks. 
Secondary objectives:
 
1. To evaluate changes in tobacco-related biomarkers of exposure (BoE) before, during and after a 6-week switch from UB to VLN cigarettes.2. To evaluate nicotine pharmacokinetics (PK) before, during and after a 6-week switch from UB to VLN cigarettes.3. To evaluate changes in subjective effects before, during and after a 6-week switch from UB cigarettes to VLN cigarettes
Study Design	
This is an open-label, non-randomized, forced-switching study to be conducted at multiple study sites. Seventy (70) self-affirmed exclusive filtered king size non-mentholated cigarette smokers and 70 self-affirmed exclusive filtered king size mentholated cigarette smokers will be enrolled and begin the study at Week -1.
 
All potential subjects will provide informed consent and successfully complete the Screening procedures prior to participation in the study. Subjects will also engage in a brief product trial with the VLN cigarettes. Subjects who react negatively (i.e., unwilling to use and/or cannot tolerate the product [experience adverse events (AEs) that will prevent them from continuing to use the product as judged by the Investigator]) to the VLN cigarettes during the product trial period will not continue in the study.
 
At the start of Week -1, all subjects will be asked to smoke their UB cigarettes as per their usual daily consumption for the following week. Subjects will receive an electronic diary (e-diary) to record daily cigarette use (cigarettes per day [CPD]). Training in completion of the e-diary will be provided at the visit at the start of Week -1.
 
Subjects will return at the end of Week -1, at the time indicated by the clinical research unit (CRU), for collection of blood and 24-hour urine samples for baseline BoE assessments. Subjective questionnaires for dependence, withdrawal symptoms, urges to smoke, and perceived health risk will also be completed at scheduled times. A subset of 18 non-menthol and 18 menthol smoker subjects will complete an assessment of puffing topography with their UB cigarettes during this visit. A further subset of 12 of the non-menthol and 12 of the menthol smoker subjects who complete the topography assessment will also complete a nicotine PK assessment at the end of this visit. Subjects who undergo topography and PK assessments will be assigned to switch to smoking VLN cigarettes.
 
On Day 1 of Week 1, subjects will be randomly selected to either remain smoking their non-menthol (20 subjects) or menthol (20 subjects) UB cigarettes, or to switch to smoking non-menthol (50 subjects) or menthol (50 subjects) VLN cigarettes as per their UB cigarette flavor. Subjects will return at the end of Weeks 2 and 6, at the time indicated by the CRU, for collection of blood and 24-hour

	
urine samples for BoE assessments. Subjective effects questionnaires will also be completed at scheduled times. Subjects will continue recording their CPD in their e-diaries. A subset of 18 non-menthol and 18 menthol smoker subjects will complete an assessment of puffing topography with the VLN cigarettes at these visits, and a further subset of 12 non-menthol and 12 menthol smoker subjects will also complete an assessment of nicotine PK at the end of these visits. Subjects undergoing topography and PK assessments will have been assigned to switch to smoking VLN cigarettes.
 
Additionally, all subjects will visit the clinic at the end of Week 4 to receive further supplies of cigarettes (if assigned to the VLN groups) and to complete subjective effects questionnaires.
 
Subjects randomized to the VLN groups will be provided with a supply of VLN cigarettes at each visit, which will be 150 % of their usual daily consumption as reported during Week -1. If a subject runs out of cigarettes between clinic visits, they may visit the clinic to receive further cigarettes. All subjects will be asked to smoke their cigarettes ad libitum, recording their actual daily consumption in their e-diaries. Non-compliant nicotine product consumption should also be recorded. Used cigarette butts will also be collected during ambulatory periods to verify product use and/or assess compliance. During Week -1 (all subjects) and all subsequent weeks (subjects randomized to continue smoking UB cigarettes) subjects will be asked not to change their UB cigarette brand or flavor.
 
The CRU will attempt to contact all subjects who participated in the study (including subjects who terminate the study early) using their standard procedures approximately 7 days after the last contact to determine if any AE has occurred since the last study visit.
  <pre> graph TD A[70 non-menthol cigarette smokers] --> B[70 menthol cigarette smokers] B --> C[50 subjects randomised to smoke non-menthol VLN cigarettes] B --> D[20 subjects randomised to continue smoking non-menthol UB cigarettes] C --> E[50 subjects randomised to smoke non-menthol VLN cigarettes] C --> F[20 subjects randomised to continue smoking non-menthol UB cigarettes] C --> G[Clinic visits²] C --> H[BoE assessments³] C --> I[Subjective measures] C --> J[Puffing topography⁴ and nicotine PKs⁵] C --> K[Armulatory periods⁶] F --> G F --> H F --> I F --> J F --> K E --> G E --> H E --> I E --> J E --> K J --> L[End of Study Week] L --> M[-1] L --> N[2] L --> O[4] L --> P[6] </pre> 
¹Including trial of VLN cigarettes. ²E-diary training at start of Week -1 ³24h urine BoE, blood COHb and plasma cotinine ⁴Subset of 18 subjects assigned to smoke non-menthol VLN cigarettes and 18 subjects assigned to smoke menthol VLN cigarettes ⁵Subset of 12 subjects assigned to smoke non-menthol VLN cigarettes and 12 subjects assigned to smoke menthol VLN cigarettes ⁶E-diary completion for cigarette consumption, and used cigarette butt collection

Study Population	Seventy (70) self-affirmed, exclusive smokers each of non-mentholated and mentholated King-size cigarettes will be enrolled into the study.

Duration of Study Conduct	Screening events will occur within 28 days prior to Day 1 of Week -1. Subjects will participate in the study for a period of 7 weeks after the start of Week -1, with a follow-up call approximately 7 days after the last study visit.
Study Products and Summarization	
The study products are:
 
• Subject's UB non-mentholated filtered king size cigarettes• Subject's UB mentholated filtered king size cigarettes• Non-mentholated VLN cigarettes• Mentholated VLN cigarettes 
VLN cigarettes contain 0.4mg nicotine per gram of tobacco.
 
Subjects will smoke their assigned products ad libitum throughout the study. Product use will be listed by subject and summarized by time point (study week).

Consumption and Biomarker Data Parameters and Summarization	
During ambulatory periods between clinic visits, subjects will record daily cigarette use (CPD) in their e-diary, including both compliant and non-compliant (nicotine containing products other than their assigned product) use. Subjects will also collect used cigarette butts during these periods.
 
Twenty-four (24)-hour urine collections will be performed during clinic visits at the end of Weeks -1, 2 and 6, for BoE (total NNAL, total NNN, 3-HPMA, S-PMA, 1-OHP and T_{neq}) analysis. Creatinine will also be measured in each 24-hour collection and may be used to adjust the concentration values of the BoE if necessary. Blood samples for carboxyhemoglobin (COHb) and cotinine measurement will also be taken during these visits.
 
All data will be listed by subject and summarized by time point using descriptive statistics.

Puffing topography Data Parameters and Summarization	
Puffing topography will be measured in a randomly-selected subset of 18 non-menthol and 18 menthol cigarette smokers during an ad libitum usage session at the clinic visits at the end of Week -1 (UB cigarette) and Weeks 2 and 6 (VLN cigarettes). These subjects will be/have been assigned to switch to smoking VLN cigarettes. Puffing topography will be assessed using the mobile smoking puff analyzer (SPA-M; Sodim) during the confinement periods. Topography assessment will only be performed at one of the two clinical sites (Lincoln).
 
The following topography parameters will be assessed:
 
• Puff duration• Puff volume• Peak puff flow rate• Average flow rate• Inter-puff interval 
All data will be listed by subject and summarized using descriptive statistics.

Nicotine PK Data Parameters and Summarization	
Plasma nicotine levels will be assessed in a subset of 12 non-menthol and 12 menthol cigarette smokers before, during and after a 5-minute ad libitum smoking session with UB (Week -1) and VLN (Weeks 2 and 6) cigarettes. These subjects will be/have been assigned to switch to smoking VLN cigarettes and will be randomly selected from the subjects selected to undergo topography assessments. Blood samples will be drawn at -5, 2, 5, 7, 10, 12, 15, 20, 30, 45, 60, 90, 120, 150 and 180 minutes relative to the start of cigarette smoking a single cigarette. Nicotine PK assessment will be performed on the day following 24-hour confined urine collection and after an overnight abstinence from cigarette smoking.
 
Plasma nicotine PK parameters, Cmax, Tmax and AUC will be computed from the individual plasma concentrations.
 
Nicotine concentrations and PK parameters will be listed by subject and summarized by study product and sex using descriptive statistics.

Subjective Effects Data Collection and Summarization	
Measurement of subjective effects will be made during the clinic visits at Weeks -1, 2, 4 and 6, with the single administration of the Fagerström Test for Cigarette Dependence (FTCD), the Brief Questionnaire of Smoking Urges (QSU-Brief), the Minnesota Nicotine Withdrawal Scale - Revised (MNWS-R) and a perceived health risk scale.
 
All data will be listed by subject and summarized by time point using descriptive statistics.

Safety Assessments and Summarization	
Baseline visit: At the start of Week -1, evaluations will include vital signs, exhaled breath CO measurement, urine drug and alcohol screen, urine cotinine test and a serum pregnancy test (females only), and body weight.
 
On study: At the end of Weeks -1, 2, 4 and 6, evaluations will include vital signs, a urine drug and alcohol screen, and a urine pregnancy test (females only). End of study (or early discontinuation) evaluations will include a 12-lead ECG and vital signs.
 
Throughout the study: AEs spontaneously reported by the subjects or observed by the Investigator or other study personnel will be monitored from after the product trial at Screening until the End of Study (or upon early discontinuation), and will be queried by study staff at the follow-up call. Any concomitant medications taken from screening through the end of study (or early discontinuation) will also be recorded. A symptom-driven physical examination may be performed at any time, at the discretion of the Investigator or designee.
 
AEs will be tabulated and summary statistics for vital signs and clinical laboratory tests may be computed and provided, as deemed clinically appropriate.

SUMMARY OF STUDY EVENTS

STUDY EVENTS/ASSESSMENTS	Screening ¹	Clinic Visits					Out-of-CRU Between Clinic Visits	End of study ²	Follow-up Call ³
		Start of Week -1	End of Week -1 (baseline)	End of Week 2	End of Week 4	End of Week 6			
Informed Consent	X								
Demographics	X								
Smoking/Tobacco/Nicotine Product Use History	X								
Usual Brand Cigarette and Flavor Documentation ⁴	X	X	X	X ⁵	X ⁶	X ⁷			
Medical History	X								
Review of Inclusion / Exclusion Criteria	X								
Review of Concomitant Medications						X			
Physical Examination ⁸	X							X ⁹	X ¹⁰
Height, Body Weight, BMI	X	X ¹¹						X ¹²	
Vital Signs	X	X	X	X	X	X		X	
12-Lead ECG	X							X	

¹ Up to 28 days prior to first study visit (start of Week -2).

² At end of Week 6 clinic visit or upon early discontinuation.

³ Approximately 7 days after their last clinic visit, including subjects who discontinue from the study early.

⁴ Including taking a color photocopy of the front and back of the subject's UB cigarette pack along with a ruler.

⁵ For subjects randomized to continue smoking UB cigarettes only.

⁶ For subjects randomized to continue smoking UB cigarettes only.

⁷ For subjects randomized to continue smoking UB cigarettes only.

⁸ Standard physical examination including oral cavity and oropharynx. A symptom driven examination can be performed at other time, at Investigator or designee's discretion.

⁹ Symptom driven and if deemed necessary.

¹⁰ Symptom driven and if deemed necessary based on the follow-up call. Subjects will visit the clinic for this to take place.

¹¹ Body weight only at Start of Week -1

¹² Body weight only at end of study

STUDY EVENTS/ASSESSMENTS	Screening ¹	Clinic Visits					Out-of-CRU Between Clinic Visits		
		Start of Week -1	End of Week -1 (baseline)	End of Week 2	End of Week 4	End of Week 6			
Clinical Chemistry ¹³ , Hematology, Urinalysis	X							X	
Urine Drug and Alcohol Screen	X	X	X	X	X	X		X	
HIV, HBsAg, and HCV Serology	X								
Serum Pregnancy Test (females)	X								
Serum FSH Test ¹⁴	X								
Urine Cotinine Screen	X	X							
Exhaled CO Measurement	X	X							
Test Product (VLN cigarette) Trial	X								
Provide Smoking Cessation Information ¹⁵	X							X	X
Review of AEs	X ¹⁶	X	X	X	X	X		X	X
Urine Pregnancy Test (females)		X	X						
Review Restrictions on Smoking and Nicotine Product Use	X	X	X	X	X	X			
Reminder Contacts to return to the CRU ¹⁷		X ¹⁸					X ¹⁹		
Test Product Dispensing			X	X	X				

¹³ Clinical chemistry tests will be performed after at least an 8 hour fast; however, in case of dropouts or rechecks, subjects may not have fasted for 8 hours prior to the clinical chemistry sample being taken.

¹⁴ Postmenopausal females only

¹⁵ Subjects will be referred to the Quit Assist® website

¹⁶ AE recording to begin immediately after the product trial at Screening.

¹⁷ Phone calls or texts or instant messages (as per site preference) reminding subjects of clinic visits.

¹⁸ The day prior to clinic visit at start of Week -1 subjects will be contacted.

¹⁹The day prior to clinic visits at end of Weeks -1, 2, 4 and 6 subjects will be contacted.

STUDY EVENTS/ASSESSMENTS	Screening ¹	Clinic Visits					Out-of-CRU Between Clinic Visits		
		Start of Week -1	End of Week -1 (baseline)	End of Week 2	End of Week 4	End of Week 6			
Dispense Canisters for Used Cigarette Butt Collection		X	X	X	X				
Used Cigarette Butt Collection							X		
Used Cigarette Butt Canister Return			X	X	X	X			
24-hour Urine Collection for BoE analysis			X	X		X			
Plasma Sample for Cotinine Analysis			X	X		X			
Blood Sample for COHb Analysis			X	X		X			
Puffing Topography ²⁰			X	X		X			
Blood Samples for Nicotine PK Analysis ²¹			X	X		X			
Training on e-diary use		X							
Daily e-diary use to record cigarette consumption		X	X	X	X	X	X		
Fagerström Test for Cigarette Dependence (FTCD)			X	X	X	X			
Brief Questionnaire of Smoking Urges (QSU-brief)			X	X	X	X			
Minnesota Nicotine Withdrawal Scale - Revised (MNWS-R)			X	X	X	X			

²⁰ In a randomly-selected subset of 18 non-menthol and 18 menthol cigarette smokers at a single site (Lincoln). These subjects will be/have been assigned to switch to smoking VLN cigarettes. To be performed during the clinic confinement period.

²¹ In a randomly-selected subset of 12 non-menthol and 12 menthol cigarette smokers at a single site (Lincoln). These subjects will be/have been assigned to switch to smoking VLN cigarettes and will be randomly selected from the subjects selected to undergo topography assessments. To be performed on the day following 24-hour confined urine collection and after an overnight abstinence from cigarette smoking/nicotine product use.

		Clinic Visits					Out-of-CRU Between Clinic Visits		
STUDY EVENTS/ASSESSMENTS	Screening ¹	Start of Week -1	End of Week -1 (baseline)	End of Week 2	End of Week 4	End of Week 6	Weeks -1 to 6	End of study ²	Follow-up Call ³
Perceived health risk scale			X	X	X	X			
Confinement to CRU for 24 hours			X	X		X			
Ambulatory Visits to CRU	X	X			X		X		

ABBREVIATIONS

1-OHP	1-hydroxypyrene
3-HPMA	3-hydroxypropylmercapturic acid
AE	Adverse event
ANPRM	Advanced Notice of Proposed Rule Making
AUC	Area under the concentration curve
BMI	Body mass index
BoE	Biomarker of exposure
bpm	Beats per minute
°C	Degree Celsius
CDMS	Clinical Data Management System
CFR	Code of Federal Regulations
CPD	Cigarettes per day
Cmax	Maximum plasma concentration
CO	Carbon monoxide
COHb	Carboxyhemoglobin
CRF	Case report form
CRU	Clinical research unit
CV	Coefficient of variability
CYP	Cytochrome P450
e-diary	Electronic diary
ECG	Electrocardiogram
eCO	Exhaled carbon monoxide
eCRF	Electronic case report form
EDC	Electronic data capture
°F	Degree Fahrenheit
FDA	Food and Drug Administration
FSH	Follicle-stimulating hormone
FTCD	Fagerström Test for Cigarette Dependence
GCP	Good Clinical Practice
GLP	Good Laboratory Practice
HbsAg	Hepatitis B surface antigen
HCV	Hepatitis C virus

HIV	Human immunodeficiency virus
ICF	Informed consent form
ICH	International Conference on Harmonization
IRB	Institutional Review Board
ISO	International Organization for Standardization
ITT	Intent to treat
K ₂ EDTA	Dipotassium ethylenediaminetetraacetic acid

1. INTRODUCTION AND BACKGROUND

1.1 Background

A gradual reduction of nicotine levels in cigarettes was first proposed by Benowitz and Henningfield in 1994 (1). In this paper, the authors proposed a long-term (over many years) reduction in cigarette nicotine levels as a measure to reduce smoking addiction and to aid cessation for smokers. The underlying assumption of this proposal was that there is a nicotine exposure threshold, below which reinforcing effects of nicotine are insufficient to cause or sustain addiction. The absolute level of such a threshold has not yet been determined. Hatsukami et al (2) published results of a study where subjects were switched to VLN cigarettes for six weeks. Compensatory smoking behavior, biomarkers of exposure (BoE), and tobacco dependence withdrawal were assessed. VLN cigarettes did not result in compensatory smoking behavior. Cigarettes per day and biomarkers of exposure were reduced after 6 weeks. VLN cigarettes were associated with a greater relief of withdrawal than nicotine lozenges.

In March 2018, the Food and Drug Administration (FDA) announced through an Advanced Notice of Proposed Rule Making (ANPRM) that a tobacco standard for lowering nicotine in cigarettes is being considered (3). As new cigarettes with reduced amounts of nicotine in the tobacco blend are developed, clinical studies are required to assess whether they lead to reductions in cigarette consumption and whether this is associated with reductions in biomarkers of exposure to cigarette smoke toxicants and changes in cigarette dependence. Furthermore, subjective assessments of urges to smoke, withdrawal symptoms and perceived health risks are also useful indicators of whether low nicotine cigarettes will give rise to reduced addiction to cigarette smoking.

1.2 Study Purpose

The purpose of this study is to examine whether measures of cigarette consumption behavior (cigarettes per day and smoking topography) are changed when smokers switch from smoking conventional cigarettes to smoking cigarettes with a very low nicotine (VLN) content (0.4 mg nicotine per gram of tobacco). A secondary purpose is to examine changes in BoE, nicotine pharmacokinetics and subjective measures of dependence, smoking urges, withdrawal symptoms and perceived health risks, when subjects switch to smoking VLN cigarettes.

1.3 Hypothesis

It is anticipated that when adult smokers switch to smoking VLN cigarettes, after habitually consuming their usual quantity and brand of cigarettes, their daily cigarette consumption will be reduced. It is further anticipated that puffing topography parameters will be unchanged following smoking VLN cigarettes for 6 weeks *i.e.* no smoking compensation will occur.

2. STUDY OBJECTIVES

The primary objectives of this study are:

1. To characterize cigarette consumption behavior (cigarettes per day and puffing topography) before, during and after a switch from UB to VLN cigarettes for 6 weeks.

The secondary objectives of this study are:

1. To evaluate changes in tobacco-related BoE before, during and after a 6-week switch from UB to VLN cigarettes.
2. To evaluate nicotine pharmacokinetics before, during and after a 6-week switch from UB to VLN cigarettes.
3. To evaluate changes in subjective effects before, during and after a 6-week switch from UB cigarettes to VLN cigarettes.

2.1 Design and Procedures

This is an open-label, non-randomized, forced-switching study to be conducted at multiple study sites. Seventy (70) self-affirmed exclusive filtered king size non-mentholated cigarette smokers and 70 self-affirmed exclusive filtered king size mentholated cigarette smokers will be enrolled and begin the study at Week -1.

All potential subjects will provide informed consent and successfully complete the Screening procedures prior to participation in the study. Subjects will also engage in a brief product trial with the VLN cigarettes. Subjects who react negatively (i.e., unwilling to use and/or cannot tolerate the product [experience adverse events (AEs) that will prevent them from continuing to use the product as judged by the Investigator]) to the VLN cigarettes during the product trial period will not continue in the study.

At the start of Week -1, all subjects will be asked to smoke their UB cigarettes as per their usual daily consumption for the following week. Subjects will receive an electronic diary (e-diary) to record daily cigarette use (cigarettes per day [CPD]). Training in completion of the e-diary will be provided at the visit at the start of Week -1.

Subjects will return at the end of Week -1, at the time indicated by the clinical research unit (CRU), for collection of blood and 24-hour urine samples for baseline BoE assessments. Subjective questionnaires for dependence, withdrawal symptoms, urges to smoke, and perceived health risk will also be completed at scheduled times. A subset of 18 non-menthol and 18 menthol smoker subjects will complete an assessment of puffing topography with their UB cigarettes during this visit. A further subset of 12 of the non-menthol and 12 of the menthol smoker subjects who complete the topography assessment will also complete a nicotine PK assessment at the end of this visit. Subjects who undergo topography and PK assessments will be assigned to switch to smoking VLN cigarettes.

On Day 1 of Week 1, subjects will be randomly selected to either remain smoking their non-menthol (20 subjects) or menthol (20 subjects) UB cigarettes, or to switch to smoking non-menthol (50 subjects) or menthol (50 subjects) VLN cigarettes as per their UB cigarette flavor. Subjects will return at the end of Weeks 2 and 6, at the time indicated by the CRU, for collection of blood and 24-hour urine samples for BoE assessments. Subjective effects questionnaires will also be completed at scheduled times. Subjects will continue recording their CPD in their e-diaries. A subset of 18 non-menthol and 18 menthol smoker subjects will complete an assessment of puffing topography with the VLN

cigarettes at these visits, and a further subset of 12 non-menthol and 12 menthol smoker subjects will also complete an assessment of nicotine PK at the end of these visits. Subjects undergoing topography and PK assessments will have been assigned to switch to smoking VLN cigarettes.

Additionally, all subjects will visit the clinic at the end of Week 4 to receive further supplies of cigarettes (if assigned to the VLN groups) and to complete subjective effects questionnaires.

Subjects randomized to the VLN groups will be provided with a supply of VLN cigarettes at each visit, which will be 150 % of their usual daily consumption as reported during Week -1. If a subject runs out of cigarettes between clinic visits, they may visit the clinic to receive additional test cigarettes. All subjects will be asked to smoke their cigarettes *ad libitum*, recording their actual daily consumption in their e-diaries. Non-compliant nicotine product consumption should also be recorded. Used cigarette butts will also be collected during ambulatory periods to verify product use and/or assess compliance. During Week -1 (all subjects) and all subsequent weeks (subjects randomized to continue smoking UB cigarettes) subjects will be asked not to change their UB cigarette brand or flavor.

The CRU will attempt to contact all subjects who participated in the study (including subjects who terminate the study early) using their standard procedures approximately 7 days after the last contact to determine if any AE has occurred since the last study visit.

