5.12.5 Puffing topography measurements

At clinic visits at the end of Weeks -1, 2 and 6, a randomly-selected subset of 18 non-menthol and 18 menthol smoker subjects will complete a puffing topography evaluation session with either their UB (Week -1) or the VLN (Weeks 2 and 6) cigarettes. These subjects will be/have been assigned to switch to smoking VLN cigarettes. These assessments will only be performed at a single clinical site (Lincoln) and will take place during the 24-hour confinement period.

During the puffing topography assessment, subjects will engage in a 1-hour *ad libitum* smoking session with their UB (Week -1) or the VLN (Weeks 2 and 6) cigarettes. In these sessions, subjects will smoke cigarettes with the mobile smoking puff analyzer (SPA-M; Sodim). The topography device will be monitored to ensure the device is actively recording during each session.

Topography assessment will be started at least one hour following either the subject's breakfast or lunch. The puffing topography session for each subject at Weeks 2 and 6 should be within \pm 2 hours of the time of their Week -1 session.

Additional details and instructions for puffing topography procedures will be provided separately.

The following topography parameters will be assessed:

- Puff duration
- Puff volume
- Peak puff flow rate
- Average flow rate
- Inter-puff interval

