3. STUDY DESIGN

This is an open-label, randomized, forced-switching study to be conducted at multiple study sites. Seventy (70) self-affirmed exclusive filtered non-mentholated cigarette smokers and 70 self-affirmed exclusive filtered mentholated cigarette smokers will be enrolled and begin the study at Week -1.

All potential subjects will provide informed consent and successfully complete the Screening procedures prior to participation in the study. Subjects will also engage in a

brief product trial with the VLN cigarettes. Subjects who react negatively (i.e., unwilling to use and/or cannot tolerate the product [experience AEs that will prevent them from continuing to use the product as judged by the Investigator]) to the VLN cigarettes during the product trial period will not continue in the study.

At the start of Week -1, all subjects will be asked to smoke their UB cigarettes as per their usual daily consumption for the following week. Subjects will receive an e-diary to record daily cigarette use (CPD). Training in completion of the e-diary will be provided at the visit at the start of Week -1.

Subjects will return at the end of Week -1, at the time indicated by the clinical research unit (CRU), for collection of blood and 24-hour urine samples for baseline BoE assessments. Subjective questionnaires for dependence, withdrawal symptoms, urges to smoke, and perceived health risk will also be completed at scheduled times. A randomly-selected subset of 18 non-menthol and 18 menthol smoker subjects will complete an assessment of puffing topography with their UB cigarettes during this visit. A further subset of 12 of the non-menthol and 12 of the menthol smoker subjects who complete the topography assessment will also complete a nicotine PK assessment at the end of this visit. Subjects who undergo topography and PK assessments will be assigned to switch to smoking VLN cigarettes.

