7.3 Statistical Analysis of Primary Endpoints

Paired t-tests will be used to compare cigarette consumption (CPD) and puffing topography parameters at the Week 2 and Week 6 time points with the baseline (Week -1) values. This analysis will be conducted on the evaluable subjects in the PP population. If data are unexpectedly found not to be normally distributed, an appropriate non-parametric test will be performed. Differences will be considered statistically significant at an alpha level of 0.05. Means, difference of means, 90% confidence interval for difference, and p-value will be presented.

The following SAS codes will be used for the analysis:

```
Proc ttest data=<>;  
By product_group;  
Paired week_X*baseline;  
Run;
```

Where week_X will be either Week 2 or Week 6. Product Groups are VLN non-mentholated, VLN non-mentholated, and VLN combined which pooled non-mentholated and mentholated groups. The primary analysis will be based on the VLN combined product group.

In addition, a linear mixed model analysis of variance will be used to compare the between product group differences in the absolute change from baseline values of the consumption and puffing topography parameters. Product group, week, and product group by week interaction will be the fixed factors in the model. A restricted maximum likelihood estimation method with an unstructured (UN) covariance structure will be applied. If the model does not converge, the first order autoregressive AR(1) and/or compound symmetry CS covariance structures will be tested as alternatives. The least-square mean difference, 95% confidence interval and p-value will be provided for the product group difference. The pairwise comparisons (VLN non-mentholated versus UB non-mentholated, VLN mentholated versus UB mentholated, and VLN combined versus UB combined) will be performed at week Week 2 and Week 6. Least-square means (LSMeans), difference of LSMeans, 90% confidence interval for difference, and p-value for difference will be presented.

The following SAS codes will be used to perform the analysis.

```
Proc mixed data=<>;  
Class subject product_group week;  
Model response = product_group week product_group*week /ddf=kr;  
Repeated week/type=<type> subject=subject;  
LSmeans product_group*week/CL alpha=0.05 CL pdiff;  
Run;
```

The primary analysis will be the pairwise comparisons of VLN combined versus UB combined (pooled non-mentholated and mentholated groups).

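### The documents do not say how the 36 Lincoln topography/PK subjects come to VLN; if they are pre-assigned, site is unbalanced between VLN and UB and the mixed model has no site term

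*Protocol*

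**What the plan says.** Protocol 5.12.5 states that "a randomly-selected subset of 18 non-menthol and 18 menthol smoker subjects will complete a puffing topography evaluation session", and that "These assessments will only be performed at a single clinical site (Lincoln". The Synopsis confirms that Lincoln is one of two sites. The PK subset is nested: "A further subset of 12 of the non-menthol and 12 of the menthol smoker subjects who complete the topography assessment".

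Protocol 2.1 places the first session at the end of Week -1, with usual brand, and adds: "Subjects who undergo topography and PK assessments will be assigned to switch to smoking VLN cigarettes". The next step is dated later: "On Day 1 of Week 1, subjects will be randomly selected to either remain smoking their non-menthol (20 subjects", with 20 menthol smokers also staying on UB and 50 per flavour moving to VLN.

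Protocol 2.1 calls the design non-randomized. SAP 3 says "This is an open-label, randomized, forced-switching study to be conducted at multiple study sites" and dates the selection to Day -1 of Week 1. SAP 12 nevertheless describes its analyses as aligned with the Protocol.

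Protocol 4.5 refers to a randomisation scheme for the sites and names age and gender as balancing factors. It does not mention site or the subset. For the between-group model, SAP 7.3 states: "Product group, week, and product group by week interaction will be the fixed factors in the model". SAP 7.3 also names VLN combined versus UB combined as the primary analysis of that model.

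**The concern.** A group drawn from one site, and ending up wholly on one product, has its first assessment before the dated random selection. If group membership fixes the product, Lincoln subjects have a higher chance of VLN than subjects at the other site. Arm and site are then associated.

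UB is the only concurrent control for time, diary-keeping and clinic effects. If the sites differ in how CPD, biomarkers or questionnaire scores change over six weeks, part of that difference would be read as a VLN effect. For topography the question does not arise, because no UB subject is measured and there is no VLN-versus-UB contrast to bias.

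A reader also cannot tell whether 100 or 64 VLN subjects come through the 50:20 selection.

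**Working it through.** **Inputs from the documents.** Topography subset: 18 + 18 = 36. VLN: 50 + 50 = 100. UB: 20 + 20 = 40. Total: 140. The subset is 36/100 = 36% of VLN (18/50 per flavour). The stated sample size of 50 per VLN group rests on a paired test whose SD is not given, so it cannot be reproduced; it is not in question here.

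**Could the subset be picked independently of allocation?** Under a 50:20 allocation, 18 such subjects would be expected to include 18 × 50/70 = 12.9 VLN and 5.1 UB. The chance that all 18 are VLN is C(52,32)/C(70,50) = 0.0008 per flavour. So one of two mechanisms must operate.

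- *Reading A, pre-assigned.* Protocol 2.1 speaks of assignment as still to come at the Week -1 session and as already done at Weeks 2 and 6. Protocol 5.12.5 describes the sampling frame as smokers of each flavour, not VLN-allocated subjects.
- *Reading B, drawn after allocation.* The footnotes to the Synopsis design figure define the subset as subjects assigned to VLN. Protocol 5.12.5 leaves the tense open, allowing past or future assignment. The SAP's Day -1 is earlier than the Protocol's Day 1, and VLN is dispensed at the end-of-Week -1 visit (Protocol 5.4), so product must be known by the end of that visit.

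**Site balance under Reading A.** Per flavour, 70 − 18 = 52 remain, of whom 50 − 18 = 32 go to VLN and 20 to UB. Let L be the number per flavour at Lincoln (an assumption), with the 52 allocated without regard to site:

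- Lincoln share of VLN = [18 + (L − 18) × 32/52] / 50
- Lincoln share of UB = [(L − 18) × 20/52] / 20
- Gap = 0.36 × (70 − L)/52

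| L per flavour | Lincoln share of VLN | Lincoln share of UB | Gap (points) |
|---|---|---|---|
| 25 | 45% | 13% | 31 |
| 35 | 57% | 33% | 24 |
| 50 | 75% | 62% | 14 |

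The limits are 36 points at L = 18 and 0 at L = 70. At L = 35 the chance of VLN is 28.5/35 = 81% at Lincoln and 32/52 = 62% elsewhere.

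**What enters the contrast.** With no product-by-site interaction, the unadjusted VLN−UB difference equals the product effect plus gap × (Lincoln minus other-site difference in change). Each 1 CPD of site difference adds 0.31, 0.24 or 0.14 CPD at L = 25, 35 or 50. The documents give no site difference. For illustration, 2 CPD at L = 35 would add 0.48 CPD.

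**Site balance under Reading B.** A 5:2 allocation within Lincoln yields 18 VLN per flavour once L ≥ 18 × 7/5 = 25.2, so 26. No site imbalance need arise.

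**Precision, in units of the change-score SD.**

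- All 140, no site term: √(1/100 + 1/40) = 0.187.
- All 140, site term, Reading A imbalance: 1/√Σ[vu/(v+u)], where v and u are the VLN and UB numbers at each site. This gives 0.196, 0.192 and 0.190 at L = 25, 35 and 45.
- Without the 36: √(1/64 + 1/40) = 0.202, about 8% above 0.187.

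These use full enrolment; the per-protocol set will be smaller.

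**The case against.** A reader might infer that 36 of the 100 VLN subjects are not randomised and that VLN versus UB is, by design, partly a site comparison. The case against that inference is strong.

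- **No exemption is stated.** The Synopsis figure and Protocol 2.1 count 50 per flavour as randomly placed on VLN. Protocol 4.5 mentions one scheme. The discontinuation listing (SAP Appendix 16.2.1.1) carries randomisation number and date with no exception for the subset. The 32:20 split appears nowhere; it follows only under Reading A.
- **The subset is itself randomly selected.** Even if pre-assigned, its members reach VLN by chance. The consequence is a different allocation probability at each site, not 36 subjects outside chance allocation.
- **Silence is not a negative.** Protocol 4.5 does not name site, but the scheme itself is not available and may be stratified.
- **The size is undocumented.** Neither enrolment by site nor any site difference is given. The model analyses change from baseline, so stable site differences in level cancel, and the assays are run at the contractor's bioanalytical laboratories, not by each clinic.
- **The powered comparison is within group.** Protocol 6.1.1 calls the between-group comparison of consumption secondary.

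All of this stands, and it rules out the firmer claim. It does not settle which order was intended, reconcile the two documents, or put site into the model that SAP 7.3 relies on for VLN versus UB. The worry that subset members learn their product before baseline measurements finish is also unproven: the documents do not say when anyone is told.

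**Conclusion.** The order of subset selection and product allocation is not determinable from the documents, and the design label and selection day conflict. Under Reading B there need be no bias. Under Reading A the Lincoln share differs between arms by 24 points at an assumed 35 per flavour (31 to 14 points for 25 to 50). That fraction of any site difference in change would pass into the VLN-versus-UB estimates for CPD, biomarkers and questionnaires.

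A CPD figure for the bias should not be quoted as a finding, since it multiplies two unknowns: enrolment at Lincoln and the site difference. The within-group paired tests, in which each subject is their own control, do not depend on this allocation. The point is worth acting on because the remedy is cheap and works under either reading.

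**What to change.** 1. Allocate all 70 subjects per flavour 50:20 from one pre-generated list stratified by site and flavour.
2. Draw the 18 topography subjects, and 12 of them for PK, at random from Lincoln subjects already allocated to VLN. State this order in Protocol 2.1, 4.5 and 5.12.5.
3. Do not disclose allocation to subjects until their end-of-Week -1 measurements are complete. Because subset membership implies VLN, it should not be explained to them in those terms beforehand.
4. Add site as a fixed effect in the SAP 7.3 mixed model, and wherever the SAP reuses that model.
5. Reconcile the design label (non-randomized or randomized) and the selection day (Day 1 or Day -1).
6. If the subset was in fact pre-assigned, keep all 140 with the site term and report VLN versus UB without the 36 (64 versus 40) as a sensitivity analysis.

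**Cost.** No added subjects or procedures. Where allocation is already unbalanced, the site term raises the SE from 0.187 to about 0.190–0.196 SD. Under exact 5:2 stratification the balance is kept and the SE stays at 0.187. The sensitivity analysis has an SE about 8% higher. Lincoln must enrol about 26 or more per flavour.
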